7.7.1.2 Long Term Treatment Phase

There will be two key co-secondary endpoints of efficacy assessed during the Long Term Treatment Phase. The first is:

- Clinical symptom remission defined by (1) the total number of liquid/very soft stools for the 7 days prior to the Week 52 visit being ≤ 10 (from CDAI Item 1); AND (2) an abdominal pain rating of ≤ 1 (from CDAI Item 2) on each day for the 7 days prior to the Week 52 visit.

The second is:

- Endoscopic remission defined as a SES-CD score of ≤ 2 at Week 52. SES-CD scores will be calculated from centrally-read digital video of ileocolonoscopies performed at Week 52.

For each endpoint, the number and proportion of subjects with clinical and endoscopic remission will be summarized by treatment group.

For each endpoint, the null hypothesis $H_0: \pi_R - \pi_P = 0$ versus the alternative $H_A: \pi_R - \pi_P \neq 0$ is of interest, where π_R is the binomial parameter for remission for the Rifaximin DR group, and π_P is the binomial parameter for remission for the placebo group. Subjects who require the initiation of rescue medication and/or surgery for CD will be considered treatment failures from the date of the introduction of the rescue medication and/or surgery, regardless of their actual response data. The Cochran-Mantel-Haenszel (CMH) test, stratified by country, will be used to test the hypothesis. Each null hypothesis of no difference will be rejected if the resulting p-value for the respective statistical test is less than 0.05. Significance for clinical and endoscopic remission will only be declared if both null hypotheses are rejected. As such, the overall Type I error rate will be maintained at the 5% level without adjustment for multiple comparisons.

If it is evident that the response variable is confounded with some of the background variables, then logistic regression will be performed using the background variables as covariates. The differences between this adjusted analysis and the previous unadjusted analysis will be noted, and the impact of such differences will be discussed.

7.7.2 Secondary Efficacy Analysis

7.7.2.1 Binary outcomes

Analysis of binary endpoints will be based on the methods outlined above for the primary efficacy analysis. It includes:

- Induction of clinical remission defined as a CDAI Score of less than 150 points at Week 16.
- Clinical symptom remission over time: The total number of liquid/very soft stools for the 7 days prior to each clinic visit being ≤ 10 ; AND (2) an abdominal pain rating of ≤ 1 on each day for the last 7 days prior to each clinic visit in $\geq 80\%$ of the study visits during the 52-Week Treatment Period, including Week 52.
- Proportion of subjects with response to the abdominal pain component of the co-primary endpoint at post-baseline time points.

- Proportion of subjects with response to the liquid/very soft stool component of the co-primary endpoint at post-baseline time points.
- Proportion of subjects with SES-CD score of 0 at Week 52.
- Proportion of subjects who achieve clinical remission by the CDAI endpoint at post-baseline time points.
- Percentage of subjects who achieve clinical response at post-baseline time points.
Clinical response is defined as a reduction of at least 100 points from the baseline CDAI score.

7.7.2.2 Time to durable response

Time until durable response endpoints include:

- Time until durable response to the liquid/very soft stool component of the co-primary endpoint during the 52-Week Treatment Period.
- Time until durable response to the abdominal pain component of the co-primary endpoint during the 52-Week Treatment Period.

For time until durable response to the liquid/very soft stool component of the co-primary endpoint during the 52-Week Treatment Phase, a response will be considered durable if it started at Week 4 and lasted through Week 52. A response is defined as total number of liquid/very soft stools for the 7 days prior to the visit being ≤ 10 (from CDAI Item 1). The endpoint is then the time when the durable response began, or the first week of response that began the string of consecutive visits with response through Week 52. It is worth remarking that this endpoint would not be defined for a subject who does not have a durable response, so we consider instead the time of the last visit at which response was achieved. For example, if a subject is categorized as a responder at Week 52, then a durable response was not achieved.

If a subject is categorized as a responder at Week 20, then a durable response started on Week 24.

Time until durable response will be analyzed by the Kolmogorov-Smirnov test. Time until durable response to the abdominal pain component of the co-primary endpoint during the 52-

Week Treatment Phase is analyzed similarly. A response is defined as abdominal pain rating of \leq 1 (from CDAI Item 2) on each day for the 7 days prior to the visit.

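### As written, the rule and examples for time until durable response reverse the endpoint that the SAP itself defines, probably through a dropped negation

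*SAP*

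**What the plan says.** SAP 7.7.2.2 covers two secondary endpoints: time until durable response on the liquid/very soft stool component, and the same on the abdominal pain component. It makes five statements, in this order:

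1. Durability: "a response will be considered durable if it started at Week 4 and lasted through Week 52".
2. Onset: the time when the durable response began, that is, "the first week of response that began the string of consecutive visits with response through Week 52".
3. Substitute rule: because "this endpoint would not be defined for a subject who does not have a durable response", the text continues "so we consider instead the time of the last visit at which response was achieved".
4. Two examples: "if a subject is categorized as a responder at Week 52, then a durable response was not achieved"; and "If a subject is categorized as a responder at Week 20, then a durable response started on Week 24".
5. Test: "Time until durable response will be analyzed by the Kolmogorov-Smirnov test".

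Protocol 8.6.2 has the same rule and examples, so it does not settle the matter. SAP section 8, which lists departures from the protocol, does not mention this endpoint. The endpoint list in SAP 4.3 refers the reader to Section 7.2 for the definition, but 7.2 is Randomization and Unblinding.

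**The concern.** The second statement requires response at Week 52. The first example denies durability to exactly the subjects who meet that requirement. The second example gives a durable onset to a subject described only as responding at Week 20, and the substitute rule looks for the last visit with response, not the last visit without it. A programmer who follows the rule and examples therefore builds something close to the complement of the intended endpoint.

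The first statement adds a separate conflict. Read strictly, it allows a single onset, Week 4, which leaves no time to analyse and does not fit an example whose onset is Week 24.

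At stake are the classification and the reported times for these two endpoints. If the primary endpoints are not significant, SAP 7.7.2.4 makes all secondary endpoints descriptive, but a descriptive table would carry the same misclassification.

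**Working it through.** No sample size, power or alpha enters this point. The check counts response patterns.

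**Inputs.** The SAP 5.1 schedule has visits at Weeks 2, 4, 8, 12 and 16, then every four weeks to Week 52. From Week 4 that is 13 visits. Each visit is a response or a non-response, so there are 2^13 = 8192 patterns.

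**Definition (run reaching Week 52).** A pattern is durable if and only if Week 52 is a response; the other 12 visits are free. Durable patterns: 2^12 = 4096. This counts a response seen only at the end of the series as a run with onset at Week 52.

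**Rule and examples taken literally, for every subject.** A pattern is called durable if its last response falls before Week 52. That requires non-response at Week 52 (4096 patterns) and at least one earlier response (remove the one pattern with none): 4096 − 1 = 4095. Every one of these has non-response at Week 52, so the overlap with the definition is 0. For all 4096 truly durable patterns, the last visit with response is Week 52, whatever the onset.

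**The Week 20 example.** If the last response is at Week 20, Weeks 24 to 52 are non-responses and Weeks 4, 8, 12 and 16 are free: 2^4 = 16 patterns. None of the 16 is durable, although the example says durable response started.

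**Substitute confined to subjects without durable response.** True durable responders keep their onset. Of the 4096 non-durable patterns, 4095 have some response and so receive a finite time. A subject whose last response is at Week 8 gets Week 8, an earlier time than a subject in durable response from Week 24.

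**Negation restored.** Take the last visit *without* response.
- If it is Week 52, there is no durable response.
- Otherwise onset is the next visit. A last non-response at Week 20 gives onset at Week 24 in 16 of 16 patterns, as the example intends.
- The pattern with response at every visit has no such visit. Without a convention the rule matches the definition in 8191 of 8192 patterns; with onset set to the first visit it matches in 8192 of 8192.
- The last non-response visit itself equals the onset in 0 of 4096 durable patterns, because it is always one visit early.

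Adding Week 2 to the grid gives the same agreement under the same convention (16,384 of 16,384).

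**Strict Week 4 start.** Only the pattern with response at all 13 visits qualifies: 1 of 8192, always timed at Week 4.

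| Rule | Patterns called durable | Of these, durable by the definition |
|---|---|---|
| Run reaching Week 52 | 4096 | 4096 |
| Rule and examples as written | 4095 | 0 |
| Negation restored, with convention | 4096 | 4096 |
| Strict Week 4 start | 1 | 1 |

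**The case against.** The best answer is that this is a transparent slip. Restore the negation and the rule and examples say what the definition says, and a competent programmer would see that. This largely stands. A reader might conclude that no reading of the section yields a usable endpoint; the documents do not support that, because the negated reading works. What does not stand is that nothing need be done. The slip occurs three times in the same direction and was carried from protocol to SAP. A silent repair would depart from the written plan, whereas SAP section 2 says changes to its methods will be documented in the study report. The negation alone also leaves open which visit is reported, what happens to a subject with response throughout, and the Week 4 sentence.

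A reader might also infer that someone who loses response after Week 20 is certain to be timed at Week 24, level with a true Week 24 onset. The substitute sentence alone gives Week 20. Week 24 arises only by combining it with the second example, which speaks of a durable response and so cannot describe that subject. The narrower point, that lost responses receive finite times, is unaffected.

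Finally, the counts weight all patterns equally and are not proportions of subjects. It is tempting to go on to a reversed treatment comparison or a stated loss of power. The documents give no visit-level rates for either component, no within-subject correlation and no achieved sample size (SAP 7.3 says both studies stop early), so neither can be claimed.

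**Conclusion.** The contradiction is real and follows from the text alone. As written, the substitute rule and both examples are the reverse of the run definition: 4095 patterns called durable, none of them among the 4096 that are. Confining the substitute to subjects without durable response avoids the reversal but mixes lost responses with true onsets. The Week 4 sentence is a further, smaller conflict.

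The counts assume complete data at the 13 visits and that a response first seen at Week 52 counts as a run. The dropped negation is an inference from how exactly it repairs the text; the documents do not say so, nor do they show that anyone would program the literal version.

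The scope is two secondary endpoints. The co-primary and key co-secondary analyses do not use this rule. A reader might go further, since protocol 8.7.5 tests secondary endpoints in order and these two stand third and fourth in protocol 2.2.3. SAP 7.11 does not carry that order forward, so the documents do not establish that later tests depend on these. The section should be corrected before unblinding.

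**What to change.** In SAP 7.7.2.2, before unblinding, with an entry in section 8 as a change from the protocol text:

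1. Insert *not* before *achieved* in the substitute rule, and change *responder* to *non-responder* in both examples.
2. State that the analysis time is the visit after the last non-response visit; that a subject with response at every visit has onset at the first qualifying visit; and that a Week 52 non-responder has no durable response and is ranked worst, or censored, by a stated rule. The choice of reported visit does not change the ordering of subjects, and so does not change the Kolmogorov-Smirnov result, but it shifts every reported onset by one visit.
3. Reconcile the Week 4 sentence with the run definition, for example by requiring a start at or after Week 4. Say how a run already present at Week 2 and a response seen only at Week 52 are treated.

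Programming check: under the same missing-data rule, the durable count for a component cannot exceed its Week 52 responder count. For stool, that count comes from the SAP 7.7.2.1 analysis "Proportion of subjects with response to the liquid/very soft stool component of the co-primary endpoint at post-baseline time points".

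The cost is three wording changes, a few stated conventions and one line in section 8. No new data and no protocol amendment are needed.

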### **3.0 INVESTIGATIONAL PLAN**

#### **3.1 Overview of Study Design**

RECD3126 is a double-blind, placebo-controlled, parallel-group, multicenter, multiregional, 52-week study to assess the efficacy and safety of Rifaximin DR tablets for the induction of clinical remission and endoscopic response at 16 weeks followed by clinical and endoscopic remission after 52 weeks of continuous therapy in subjects with active moderate Crohn's disease. Subjects with active, moderate disease defined by a CDAI score of  $\geq 220$  and  $\leq 450$  points at screening, and evidence of active ileocolonic Crohn's disease defined by a minimum SES-CD of 7 determined during baseline ileocolonoscopy will be eligible for the study.

Eligible subjects will complete a 2- to 3-week Screening Period, a 52-week Treatment Period consisting of a 16-week Induction Phase and 36-Week Long Term Treatment Phase, and a 2-week Follow-up Period. Subjects who successfully complete the 2- to 3-week Screening Period and qualify based on CDAI and SES-CD scores will enter the 52-week Treatment Period of the trial and will be randomized in a 1:1 allocation to Rifaximin DR 800 mg BID or placebo. Randomized subjects will have subsequent ileocolonoscopies conducted at the end of the Induction Phase (between Weeks 16 and 17), and following completion of the 36-week Long Term Treatment Phase (Week 52) to assess the effects of treatment on the degree of mucosal healing. Assessments of efficacy and safety will be performed during clinic visits at Weeks 0 (baseline), 2, 4, 8, 12, and 16; then every four weeks through Week 52. All subjects will complete a 2-week (study drug free) Follow-up Period following completion of the 52-week Treatment Period, and will return to the clinic for final assessments (End-of-Study [EOS] visit; Week 54). See Figure 1.

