#### **8.7.5      Multiple Comparisons/Multiplicity**

The study has a single primary endpoint as the primary hypothesis, therefore no multiplicity adjustment is needed to the overall significance level of 0.05. Additionally, the clinical trial will be providing data for two separate indications (induction and long term treatment) with each indication having its own separate endpoint. On that basis, no multiplicity adjustment is needed to the overall significance level of 0.05 per indication because conclusions will be reached independently for induction and separately for long term treatment.

The complete evaluation of clinical efficacy in this study requires the study of multiple key secondary efficacy variables collected at numerous time points. It is therefore necessary to properly and sensitively control the probability of making erroneous conclusions based solely upon compounding the likelihood of a type I error. The issue of multiplicity of secondary measurements will be handled by statistical testing of these outcomes in a hierarchical fashion. The order of secondary endpoints for the Induction and Long Term Treatment Phases are described in Sections 2.2.2 and 2.2.3. Significance tests will be conducted until a non-significant p-value is found ( $p > 0.05$ ). Once a non-significant p-value occurred, all subsequent significance tests will be considered exploratory in nature.

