7.7 Efficacy Analysis

The phrases 'statistical analysis' or 'analysis' will be used to mean inferential analysis (such as performing tests of significance, reporting p-values and confidence intervals). When no inferential analysis will be performed, the phrases 'descriptive analysis' or 'descriptive statistics' will be used (for instance, producing summary tables of means, standard deviations, percentages of responders). All efficacy analyses will be conducted on ITT population. All efficacy analyses will adjust for country.

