7.7.1 Primary Efficacy Analysis

7.7.1.1 Induction Phase

There will be two co-primary measures of efficacy assessed during the Induction Phase. The first co-primary endpoint is:

- Clinical symptom remission defined by (1) the total number of liquid/very soft stools for the 7 days prior to the Week 16 visit being ≤ 10 (from CDAI Item 1); AND (2) an

abdominal pain rating of ≤ 1 (from CDAI Item 2) on each day for the 7 days prior to the Week 16 visit.

The second co-primary endpoint is:

- Endoscopic response defined as a ≥ 3 -point decrease in the SES-CD from baseline to the SES-CD score obtained between Week 16 and Week 17. SES-CD scores will be calculated from centrally-read digital video of ileocolonoscopies performed at baseline and between Week 16 and Week 17.

For each endpoint, the null hypothesis $H_0: \pi_R - \pi_P = 0$ versus the alternative $H_A: \pi_R - \pi_P \neq 0$ is of interest, where π_R is the binomial parameter for induction of remission/response for the Rifaximin DR group, and π_P is the binomial parameter for induction of remission/response for the placebo group. Subjects who require the initiation of rescue medication and/or surgery for CD will be considered treatment failures from the date of the introduction of the rescue medication and/or surgery, regardless of their actual response data. The Cochran-Mantel-Haenszel (CMH) test, stratified by country, will be used to test the hypothesis. Each null hypothesis of no difference will be rejected if the resulting p-value for the respective statistical test is less than 0.05. Significance for the induction claim will only be declared if both null hypotheses are rejected. As such, the overall Type I error rate will be maintained at the 5% level without adjustment for multiple comparisons.

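### Time until durable response is tested by a Kolmogorov-Smirnov test without the country adjustment the SAP requires, and its usual p-value is conservative on so heavily tied an outcome

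*SAP*

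**What the plan says.** SAP 7.7.2.2, with matching text in protocol 8.6.2, covers two endpoints: time until durable response for the stool component and for the abdominal pain component. On the test it says only "Time until durable response will be analyzed by the Kolmogorov-Smirnov test". It does not say whether the p-value is asymptotic or exact, how ties are handled, or how country enters. SAP 7.7 sets a general rule: "All efficacy analyses will adjust for country". Protocol 8.6 has the same rule.

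The endpoint is the time when the durable response began, explained as "the first week of response that began the string of consecutive visits with response through Week 52". The same paragraph also says "a response will be considered durable if it started at Week 4 and lasted through Week 52". It concedes that "this endpoint would not be defined for a subject who does not have a durable response", and gives such a subject the time of their last responding visit. Two examples follow. A Week 52 responder is said not to have a durable response, and a Week 20 responder is said to have one that starts at Week 24.

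The neighbouring time-to-event endpoints (SAP 7.7.2.4) use Kaplan-Meier analysis stratified by country. That section also makes all secondary endpoints descriptive if the primary endpoints are not significant.

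**The concern.** There are two problems. The first needs no calculation: a plain two-sample Kolmogorov-Smirnov test has no country term, so the sentence that names it breaks the SAP's own rule.

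The second is calibration. The standard Kolmogorov-Smirnov p-value is derived for continuous data. Protocol 3.1 schedules "clinic visits at Weeks 0 (baseline), 2, 4, 8, 12, and 16; then every four weeks through Week 52", so the outcome can fall only on visit weeks, and everyone without a durable response shares one further value. With heavy ties the test rejects less often than its nominal level, and power can suffer.

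What is at stake is a missed secondary result. In protocol 8.7.5 secondary endpoints follow the order of protocol 2.2.2 and 2.2.3, and "Significance tests will be conducted until a non-significant p-value is found". The two durable-response endpoints are the third and fourth entries in 2.2.3, behind the key co-secondary pair in 2.2.2. A non-significant result there would make every later test exploratory.

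**Working it through.** **Inputs from the documents.** Possible start visits are Weeks 4, 8, …, 52, which is 13 values, plus one value for no durable response. For the primary analysis SAP 7.7.1.1 says "Each null hypothesis of no difference will be rejected if the resulting p-value for the respective statistical test is less than 0.05"; protocol 8.7.5 also uses 0.05 for the secondary sequence. Planned size is 330 per arm. SAP 7.3 says both studies will end early, so actual numbers may differ.

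**Inputs the documents do not give.** These are the share without a durable response and the distribution of onset times. Both are assumed here, over ranges. No size or power is stated for this test. The only comparable figure is at least 90% power for each co-primary endpoint (240 per arm, 40% vs 55%). It reproduces at 91.1%, but those are Week 16 rates, not rates of a single component held to Week 52. Borrowing the 40% placebo rate gives 1 − 0.40 = 60% tied. Counting 20% dropout as failures gives 1 − 0.40 × 0.80 = 68% tied, and 0.55 × 0.80 = 44% durable on active.

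**Hand check, binary reading (start at Week 4 or not at all).** The asymptotic test rejects when the largest gap between the two cumulative distributions exceeds 1.358 × √(2/n).
- Size. With share q not achieving, the standardised threshold is 1.358/√(q(1 − q)), whatever n is. For q = 0.6: 1.358/0.490 = 2.77, two-sided size about 0.6%. For q = 0.8: 1.358/0.4 = 3.40, about 0.07%.
- Power at n = 330, 20% vs 30%. The threshold is 1.358 × √(2/330) = 0.106. A two-proportion test needs 1.96 × √(2 × 0.25 × 0.75/330) = 0.066. The standard error of the difference is √((0.16 + 0.21)/330) = 0.0335. Power is Φ((0.100 − 0.106)/0.0335) ≈ 43% against Φ((0.100 − 0.066)/0.0335) ≈ 84%.

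**Simulated size, 13 visit values plus one tie.** Asymptotic p-value, nominal 5%, 210–330 per arm, uniform, early and late onset:

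| Share with no durable response | True size |
|---|---|
| 40–45% | 1.4–2.3% |
| 50% | 1.2–2.0% |
| 60% | 0.8–1.5% |
| 65% | 0.6–1.1% |
| 70% | 0.4–0.7% |
| 80% | 0.1–0.2% |

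At 30–40% tied it reaches about 2.5%. On the same data log-rank has size 4.6–5.5% and tie-corrected Wilcoxon 4.6–5.3%. A permutation Kolmogorov-Smirnov test has 5.5% (400 runs, Monte Carlo standard error about 1.1 points).

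**Simulated power when the share achieving durable response differs:**

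| Durable, placebo vs active | n per arm | Kolmogorov-Smirnov | Wilcoxon | Log-rank |
|---|---|---|---|---|
| 20% vs 30% | 330 | 46–49% | 83–84% | not run |
| 20% vs 30% | 100 | 6–7% | 36–37% | not run |
| 32% vs 44% | 330 | 70–71% | 86–87% | 88% |
| 32% vs 44% | 100 | 16–18% | 39–40% | 41% |
| 40% vs 55% | 330 | 89–91% | 95% | 97% |
| 40% vs 55% | 240 | 77–78% | 87–88% | 90% |
| 40% vs 55% | 100 | 31–33% | 51–52% | 55–56% |

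With a tie-calibrated p-value, Kolmogorov-Smirnov power in the 40% vs 55%, 240-per-arm row rises to about 89%.

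**Simulated power when only onset time differs.** With 50% not achieving in each arm, 240 per arm, and early against uniform onset, Kolmogorov-Smirnov has 96–99% and Wilcoxon 65–73%. Log-rank, run in the 99% case, has 27%.

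**The case against.** A reader might infer that the true error rate is about 1% or less because most subjects are tied. The documents do not support that: neither gives a durable-response rate for either component. At 40–50% tied the size is 1.2–2.3%. It reaches 1% only at roughly 60–65% tied, or under the literal Week 4 reading.

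A reader might also infer that the test loses power in general. It does not. The endpoint is a time, and against a pure difference in onset Kolmogorov-Smirnov is clearly the stronger test. The size problem also belongs to the asymptotic p-value, which the SAP does not specify; a permutation p-value removes it.

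The consequence is limited too. The error is conservative, so there is no false-positive risk and no effect on the primary or key secondary claims. The fixed sequence stands in protocol 8.7.5 but is not repeated in SAP 7.11, although SAP section 8 does not list it as dropped. If the primary fails, nothing here is tested at all.

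Finally, the calculation rests on one reading of a contradictory definition. If subjects without a durable response took the time of their last responding visit, as the text literally says, they would be spread over visits and not tied.

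All of this narrows the point. It does not remove the conflict with the country rule, or the need to specify a p-value valid under ties.

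**Conclusion.** The point holds in a limited form. The conflict between SAP 7.7.2.2 and the country rule in SAP 7.7 is plain from the text. The asymptotic Kolmogorov-Smirnov test would run at about 0.1–2.5% at nominal 5%. When the arms differ in the share achieving durable response, the loss against a rank test at 330 per arm is 4–6 points (40% vs 55%) to 35–38 points (20% vs 30%). The relative loss grows at smaller sizes: at 100 per arm and 20% vs 30%, about a fifth of the rank test's power remains.

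These sizes assume the asymptotic p-value, the reading of the endpoint as the start of the unbroken run through Week 52, and assumed tie shares and onset shapes. The matter is worth correcting before analysis. It does not threaten the trial's main conclusions.

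**What to change.** 1. Reconcile the definition in SAP 7.7.2.2 first. The Week 4 start rule, the variable start visit, the value given to subjects without a durable response, and the Week 52 and Week 20 examples cannot all stand. No test can be programmed until they agree. State also how missing visits count for this endpoint: the worst-case rule in SAP 7.10.1 is written for the primary and key secondary endpoints only.
2. Replace the test with one of two options. One is a log-rank test stratified by country, censoring subjects without a durable response at Week 52, with the Kaplan-Meier estimates already used in SAP 7.7.2.4. The other is a van Elteren test by country, ranking those subjects last.
3. If Kolmogorov-Smirnov is kept, specify a permutation p-value with treatment labels permuted within country.
4. State in SAP 7.11 whether the protocol 8.7.5 sequence still applies.

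The cost is a short rewrite of one SAP subsection and standard software, with no new data. The statistical cost is less power against pure onset-time differences, and the log-rank test gives up more than the rank test there (27% against 73% in the same simulated case). The choice should follow from whether the share achieving or the timing of durable response is of main interest, and should be made before unblinding.
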